### **8.3 Reporting Procedures for All Adverse Events (AEs)**

All participating investigators will assess the occurrence of AEs throughout the subject's participation in the study. Subjects will be followed for toxicity for 30 days after treatment has been discontinued or until death, whichever occurs first. The clinical course of each event will be followed until resolution, stabilization, or until it has been determined that the study treatment or participation is not the cause.

The investigator is responsible for ensuring that all adverse events observed by the investigator or reported by the subject which occur after the subject has signed the informed consent are fully recorded in the subject's case report form, subject's medical records, and/or any other institutional requirement. Source documentation must be available to support all adverse events.

A laboratory test abnormality considered clinically relevant (e.g., causing the subject to withdraw from the study), requiring treatment or causing apparent clinical manifestations, or judged relevant by the investigator, should be reported as an adverse event.

The investigator will provide the following for all adverse events:

- Description of the event
- Date of onset and resolution
- Grade of toxicity
- Attribution of relatedness to the investigational agent
- Action taken as a result of the event
- Outcome of event

In this study, descriptions and grading scales found in the NCI Common Terminology Criteria for Adverse Events (CTCAE) version 4.0 available at <http://ctep.cancer.gov> will be utilized for AE reporting.

Investigative sites will report adverse events to their respective IRB according to the local IRB's policies and procedures in reporting adverse events.

#### **8.4 SAE Report Form**

SAEs will be recorded on the FDA Form 3500A (MedWatch) but should only be reported as instructed below. The electronic FDA SAE reporting forms should not be used.

#### **8.5 Reporting Procedures for Serious Adverse Events**

For the purposes of safety reporting, all adverse events will be reported that occur from day of registration through 30 days after the final dose of study drug. Adverse events, both serious and non-serious, and deaths that occur during this period will be recorded in the source documents. All SAEs should be monitored until they are resolved or are clearly determined to be due to a subject's stable or chronic condition or intercurrent illness(es). Related AEs will be followed until resolution to baseline or grade 1 or stabilization.

##### **8.5.1 SAE Reporting Requirements**

- Participating investigators (all sites) must report all serious adverse events to the Lead Site Principal Investigator (e.g. Sponsor-Investigator) within **24 hours** of discovery or notification of the event. The participating investigator must also provide follow-up information on the SAE until final resolution.
- The Lead Site Principal Investigator will review the SAE and report the event to the FDA, external collaborator(s), and IRB as applicable.
- It is the Sponsor-Investigator's responsibility (e.g. lead site PI) to ensure that ALL serious adverse events that occur on the study (e.g. ALL SAEs that occur at each enrolling institution) are reported to all participating sites.

##### **Institutional Review Board Reporting Requirements:**

- Investigative sites will report adverse events to their respective IRB according to the local IRB's policies and procedures in reporting adverse events.

#### **8.6 SAEs and OnCore**

- All SAEs will be entered into OnCore.
- A copy of the SAE form(s) submitted to the sponsor-investigator is also uploaded into Oncore.

#### **8.7 Data Safety and Toxicity Committee**

It is the responsibility of each site PI to ensure that ALL SAEs occurring on this trial (internal or external) are reported to the Case Comprehensive Cancer Center's Data and Safety Toxicity Committee. This submission is simultaneous with their submission to the sponsor and/or other regulatory bodies

The sponsor-investigator is responsible for submitting an annual report to the DSTC as per CCCC Data and Safety Monitoring Plan.

## **8.8 Data and Safety Monitoring Plan**

This protocol will adhere to the policies of the Case Comprehensive Cancer Center Data and Safety Monitoring Plan in accordance with NCI guidelines.

## **9.0 PHARMACEUTICAL INFORMATION**

A list of the adverse events and potential risks associated with the investigational or commercial agents administered in this study can be found in Section 8.0.

**9.1 Name of Agent:** Halaven®

**Chemical Name:** Eribulin mesylate

**Other Names:** None

**Classification:** Antineoplastic drug

**Molecular Formula:** C40H59NO11•CH4O3S

**Mode of Action:** Microtubule Inhibitor

**Metabolism:** Unchanged eribulin mesylate was the major circulating species in plasma following administration of 14C-eribulin to patients. Metabolite concentrations represented <0.6% of parent compound, confirming that there are no major human metabolites

**Product description:** Eribulin mesylate is a microtubule inhibitor which is FDA approved for metastatic breast cancer in patients previously exposed to taxane and anthracycline

**Solution preparation:** Each vial contains 1 mg of eribulin as a 0.5-mg/mL solution in a 5:95 ratio of ethanol to water

**Storage requirements:** Room temperature

**Stability:** Soluble in water

**Route of administration:** IV

**The cost of this agent will be covered by a grant from Eisai, Incorporated.**

**Drug Accountability:** The investigator or designated study personnel are responsible for maintaining accurate dispensing records of the study drug. All study drugs must be accounted for, including study drug accidentally or deliberately destroyed. Under no circumstances will the investigator allow the

investigational drug to be used other than as directed by the protocol. If appropriate, drug storage, drug dispensing, and drug accountability may be delegated to the pharmacy section of the investigative site.

**Drug Destruction:** At the completion of the study, there will be a final reconciliation of drug shipped, drug consumed, and drug remaining. This reconciliation will be logged on the drug reconciliation form, signed and dated. Any discrepancies noted will be investigated, resolved, and documented prior to return or destruction of unused study drug. Drug destroyed on site will be documented in the study files.

## 10.0 STUDY PARAMETERS AND CALENDAR

### 10.1 Screening Evaluation

Screening studies and evaluations will be used to determine the eligibility of each subject for study inclusion.

Baseline imaging evaluations must be completed within 30 days prior to administration of protocol therapy. All other evaluations must be completed  $\leq$  7 days prior to administration of protocol therapy.

- Informed Consent
- Demographics
- Medical History
- Complete physical examination
- Height
- Weight
- Vital signs including: blood pressure, pulse, temperature, and respiratory rate
- Concomitant Medications Assessment including prescription medications, OTC, and nutritional/herbal supplements.
- Karnofsky Performance status
- Baseline Symptoms Assessment
- MRI of the brain with and without contrast
- CT, chest abdomen and pelvis with IV contrast, or total body FDG PET scan
- EKG
- Laboratory Studies:
  - Complete Blood Count (CBC) with differential and platelets.
  - Serum Chemistries: albumin, alkaline phosphatase, total bilirubin, bicarbonate, BUN, calcium, chloride, creatinine, glucose, potassium, total protein, SGOT [AST], SGPT [ALT], sodium
  - Prothrombin time/INR for calculation of Pugh-Child classification of hepatic dysfunction
  - $\beta$ -HCG for women of childbearing potential
  - Prothrombin time/INR

### **10.1.1 Treatment Period**

Treatment cycles are 21 days long.

A visit window of up to 3 days before treatment is allowed for chemistry, coagulation and hematology labs.

A visit window of  $\pm$  7 days is allowed for 3 month MRI/CT scans and follow-up visits.

### **Cycles 1-4**

#### **Laboratory Studies: to be completed 0-3 days prior to Day 1 eribulin administration**

- Complete Blood Count (CBC) with differential and platelets.
- Serum Chemistries: albumin, alkaline phosphatase, total bilirubin, bicarbonate, BUN, calcium, chloride, creatinine, glucose, potassium, total protein, SGOT [AST], SGPT [ALT], sodium, Mg
- Calculated creatinine clearance will be done if creatinine and/or BUN are abnormal.

### **Day 1**

Cycle 1, Day 1 evaluations do not need to be repeated if screening evaluations were conducted within 3 days prior to administration of protocol therapy.

- Physical Examination
- Weight
- Vital signs including: blood pressure, pulse, temperature, and respiratory rate
- Concomitant Medications Assessment including prescription medications, OTC, and nutritional/herbal supplements.
- Karnofsky Performance status
- Eribulin administration – 1.4mg/m^2 (or adjusted dose for renal or hepatic insufficiency)
- Baseline symptoms and adverse events assessment

### **Cycles 1-4**

#### **Laboratory Studies: to be completed 0-3 days prior to Day 8 eribulin administration**

- Complete Blood Count (CBC) with differential and platelets.
- Serum Chemistries: albumin, alkaline phosphatase, total bilirubin, bicarbonate, BUN, calcium, chloride, creatinine, glucose, potassium, total protein, SGOT [AST], SGPT [ALT], sodium, Mg
- Calculated creatinine clearance will be done if creatinine and/or BUN are abnormal.

### **Day 8**

- Vital signs including: blood pressure, pulse, temperature, and respiratory rate
- Karnofsky Performance status
- Eribulin administration – 1.4mg/m^2 (or adjusted dose for renal or hepatic insufficiency)
- Adverse events assessment

### **Cycles 4+**

#### **Laboratory Studies: to be completed 0-3 days prior to Days 1 and 8 eribulin administration**

- Complete Blood Count (CBC) with differential and platelets. ALC will be calculated from CBC and differential
- Serum Chemistries: albumin, alkaline phosphatase, total bilirubin, bicarbonate, BUN, calcium, chloride, creatinine, glucose, potassium, total protein, SGOT [AST], SGPT [ALT], sodium, Mg
- Calculated creatinine clearance will be done if creatinine and/or BUN are abnormal.
- MRI of the brain with and without contrast every 12 weeks
- CT, chest abdomen and pelvis with IV contrast, or total body FDG PET scan

### **Days 1 and 8**

- Physical Exam (only day 1)
- Vital signs including: blood pressure, pulse, temperature, and respiratory rate
- Concomitant Medications Assessment including prescription medications, OTC, and nutritional/herbal supplements.
- Adverse events assessment
- Karnofksy Performance status
- Eribulin administration – 1.4mg/m^2 (or adjusted dose for renal or hepatic insufficiency)

### **30-day follow-up**

- Physical Examination
- Weight
- Vital signs including: blood pressure, pulse, temperature, and respiratory rate
- Concomitant Medications Assessment including prescription medications, OTC, and nutritional/herbal supplements.
- Adverse events assessment
- Complete Blood Count (CBC) with differential and platelets. ALC will be calculated from CBC and differential
- Serum Chemistries: albumin, alkaline phosphatase, total bilirubin, bicarbonate, BUN, calcium, chloride, creatinine, glucose, potassium, total protein, SGOT [AST], SGPT [ALT], sodium, Mg
- Calculated creatinine clearance will be done if creatinine and/or BUN are abnormal.
- Karnofksy Performance status

### **Long term follow-up (Every 3 months)**

- Physical Examination
- Weight
- Vital signs including: blood pressure, pulse, temperature, and respiratory rate
- Concomitant Medications Assessment including prescription medications, OTC, and nutritional/herbal supplements.
- Adverse events assessment
- Complete Blood Count (CBC) with differential and platelets. ALC will be calculated from CBC and differential
- Serum Chemistries: albumin, alkaline phosphatase, total bilirubin, bicarbonate, BUN, calcium, chloride, creatinine, glucose, potassium, total protein, SGOT [AST], SGPT [ALT], sodium, Mg

- Calculated creatinine clearance will be done if creatinine and/or BUN are abnormal.
- Karnofksy Performance status

## 10.2 Calendar

Study Days	Pre-Study	Cycles 1-4 Day 1	Cycles 1-4 Day 8	Cycles 4+ Days 1 and 8	30 Day Follow Up	Long term Follow-Up
REQUIRED ASSESSMENTS						
Informed Consent	X					
Demographics	X					
Medical History	X					
Height	X					
Weight	X	X		X c	X	X
Vitals (blood pressure, pulse, temperature, and respiratory rate)	X	X	X	X	X	X
Physical Examination	X	X		X c	X	X
Concomitant Medication Assessment	X	X	X	X c	X	X
Karnofksy PS	X	X	X	X	X	X
Baseline Symptoms	X	X f				
Adverse Event Assessment		X	X	X	X	X
CBC / diff / platelets/ b	X	X b	X b	X b	X	X
Serum Chemistry a,b	X	X b	X b	X b	X	X
PT/INR	X					
β-HCG, women of childbearing potential	X					
EKG	X					
DISEASE ASSESSMENT						
MRI brain with and without contrast	X			X d		
CT chest, abdomen and pelvis with IV contrast or total body FDG PET	X			X e		
TREATMENT						
Eribulin mesylate		X	X	X		

**a:** Albumin, alkaline phosphatase, total bilirubin, bicarbonate, BUN, calcium, chloride, creatinine, glucose, potassium, total protein, SGOT [AST], SGPT [ALT], sodium, Mg. Calculated creatinine clearance will be done if creatinine and/or BUN are abnormal.

**b:** Laboratory Studies: to be completed 0-3 days prior to eribulin administration

**c:** Day 1 only

**d:** MRI brain to be completed every 12 weeks while on study eribulin mesylate

**e:** CT chest/abd/pelvis or total body PET every 12 weeks in patients with systemic disease while on study eribulin mesylate.

**f:** cycle 1 day 1 only

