#### **The Day 8 dose may be delayed for a maximum of 1 week.**

If toxicities do not resolve or improve to  $\leq$  Grade 2 severity by Day 15, omit the dose.

If toxicities resolve or improve to  $\leq$  Grade 2 severity by Day 15, administer eribulin mesylate at a reduced dose and initiate the next cycle no sooner than 2 weeks later.

Recommended dose reductions: If a dose has been delayed for toxicity and toxicities have recovered to Grade 2 severity or less, resume eribulin mesylate at a reduced dose as set out in Table 1. Do not re-escalate Eribulin dose after it has been reduced.

Table 2: Recommended Dose Reductions Event Description	Recommended Eribulin Dose
Permanently reduce the 1.4 mg/m^2 eribulin mesylate dose for any of the following:	1.1 mg/m 
ANC <500/mm  for >7 days	
ANC <1,000 /mm  with fever or infection	
Platelets <25,000/mm 	
Platelets <50,000/mm  requiring transfusion	
Non-hematologic Grade 3 or 4 toxicities	
Omission or delay of Day 8 Eribulin dose in previous cycle for toxicity	
Occurrence of any event requiring permanent dose reduction while receiving 1.1 mg/m^2	0.7 mg/m 
Occurrence of any event requiring permanent dose reduction while receiving 0.7 mg/m^2	Discontinue eribulin mesylate

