#### 11.1.3 Methods for Evaluation of Measurable Disease

All measurements should be taken and recorded in metric notation using calipers. All baseline evaluations should be performed within 30 days of initiation of 1st cycle of Chemotherapy.

The same method of assessment and the same technique should be used to characterize each identified and reported lesion at baseline and during follow-up.

Conventional CT and MRI This guideline has defined measurability of lesions on CT scan based on the assumption that CT slice thickness is 5 mm or less. If CT scans have slice thickness greater than 5 mm, the minimum size for a measurable lesion should be twice the slice thickness. MRI is also acceptable in certain situations (e.g., for body scans).

Use of MRI remains a complex issue. MRI has excellent contrast, spatial, and temporal resolution; however, there are many image acquisition variables involved in MRI which greatly impact image quality, lesion conspicuity, and measurement. Furthermore, the availability of MRI is variable globally. As with CT, if an MRI is performed, the technical specifications of the scanning sequences used should be optimized for the evaluation of the type and site of disease. Furthermore, as with CT, the modality used at follow-up should be the same as was used at baseline and the lesions should be measured/assessed on the same pulse sequence. It is beyond the scope of the RECIST guidelines to prescribe specific MRI pulse sequence parameters for all scanners, body parts, and diseases. Ideally, the same type of scanner should be used and the image acquisition protocol should be followed as closely as possible to prior scans. Body scans should be performed with breath-holding techniques, if possible.

PET-CT At present, the low dose or attenuation correction CT portion of a combined PET-CT is not always of optimal diagnostic CT quality for use with RECIST measurements. However, if the site can document that the CT performed as part of a PET-CT is of identical diagnostic quality to a diagnostic CT (with IV contrast), then the CT portion of the PET-CT can be used for RECIST measurements and can be used interchangeably with conventional CT in accurately measuring

cancer lesions over time. Note, however, that the PET portion of the CT introduces additional data which may bias an investigator if is not routine or serially performed.

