##### **Time to CNS Progression**

Patients will be followed clinically and radiographically. The date at which the tumor is documented to have first enlarged (brain or systemic progression) by 25% from best response (steroid dose stable or increased, neurologically stable or worse) will be considered the date of tumor progression. Time to progression will be the interval between the date of study entry and the date of tumor progression. In the event of a discrepancy and for the purposes of analysis, the treating physician's date of tumor progression will be deemed to be correct. Tissue confirmation of CNS tumor progression by stereotactic biopsy or other surgical procedure is encouraged to rule out treatment effect as a cause of radiographic worsening. Ancillary imaging techniques such as PET imaging, perfusion MRI, or MR spectroscopy of all "recurrent" or "progressive" lesions of CNS is recommended for patients at centers with access to these technologies.

Responses in the CNS and systemic compartments will be assessed by the same criteria in order to avoid confusion in the conduct of the trial. CNS disease will be imaged by MRI with gadolinium, and systemic disease will be imaged by CT scan with IV contrast.

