## **11.2 Antitumor Effect – Non-CNS Metastases**

Although non CNS response is not the primary endpoint of this trial, subjects with measurable disease will be assessed by standard criteria. For the purposes of this study, subjects should be re-evaluated every 4 cycles of treatment.

Response and progression will be evaluated in this study using the new international criteria proposed by the revised Response Evaluation Criteria in Solid Tumors (RECIST) guideline (version 1.1) [Eur J Ca 45:228-247, 2009]. Changes in the largest diameter (unidimensional measurement) of the tumor lesions and the shortest diameter in the case of malignant lymph nodes are used in the RECIST criteria.

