**Evaluation of Non-Target lesions**

**Response Evaluation of Non-Target Lesions**

**Complete Response (CR)**

Disappearance of all non-target lesions and normalization of tumor marker level. All lymph nodes must be non-pathological in size (< 10 mm short axis).

**Note:** If tumor markers are initially above the upper normal limit, they must normalize for a subject to be considered in complete clinical response.

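### The calendar accepts FDG PET in place of contrast CT without the protocol's own diagnostic-CT condition, so a patient imaged by PET alone may be unscorable for systemic response (objective 2.2.4)

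*Combined protocol and SAP*

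**What the plan says.** **Schedule.** Screening (Section 10.1) asks for "CT, chest abdomen and pelvis with IV contrast, or total body FDG PET scan". The Cycles 4+ list in Section 10.1.1 repeats this item, and the calendar row in Section 10.2 reads "CT chest, abdomen and pelvis with IV contrast or total body FDG PET". Footnote e sets the interval: "CT chest/abd/pelvis or total body PET every 12 weeks in patients with systemic disease while on study eribulin mesylate". None of these entries puts a condition on PET.

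**Measurement.** Section 11.1.4 (Time to CNS Progression) states that "systemic disease will be imaged by CT scan with IV contrast" and does not mention PET. Section 11.1.3 warns that the low-dose CT in a PET-CT "is not always of optimal diagnostic CT quality for use with RECIST measurements". It allows that CT only where the site can document that it matches a diagnostic CT with IV contrast. The same section requires one method and technique for each lesion at baseline and follow-up.

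**Scoring.** Section 11.2 scores systemic disease by RECIST 1.1 diameters. Section 11.2.1 requires measurable disease at baseline for a patient to be evaluable for objective response.

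**Tumour markers.** In Section 11.2.3, complete response of non-target lesions carries the note "If tumor markers are initially above the upper normal limit, they must normalize for a subject to be considered in complete clinical response".

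**The concern.** Objective 2.2.4 promises a systemic response rate and a duration of response. Section 13.1 adds a 95% CI and a Kaplan-Meier analysis. All of these rest on sums of lesion diameters.

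A site that works from the calendar may image a patient by PET alone and be fully compliant, yet leave nothing that RECIST can use. A missed baseline measurement cannot be recovered later. The calendar also lets a patient move from CT at baseline to PET at follow-up, which Section 11.1.3 rules out.

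Patients would then leave the systemic response analysis, or be scored on unsuitable images, because of the scan they happened to have. The safeguard is also easy to miss. It stands in Section 11.1, under the CNS heading, and Section 11.2 has no imaging-methods subsection of its own.

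**Working it through.** **1. Imaging provisions side by side**

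| Place | Systemic imaging accepted | Condition on PET |
|---|---|---|
| 10.1 Screening | contrast CT or FDG PET | none |
| 10.1.1 Cycles 4+ | contrast CT or FDG PET | none |
| 10.2 Calendar and footnote e | contrast CT or FDG PET | none |
| 11.1.4 Time to CNS Progression | contrast CT | PET not mentioned |
| 11.1.3 PET-CT | CT part of a PET-CT | documented diagnostic quality with IV contrast |
| 11.2.2 Measurable disease | chest x-ray, CT or calipers | PET not listed |

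**2. What a PET-only patient can be scored for**

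- Systemic partial response needs at least a 30% fall in the sum of diameters from baseline (11.2.3).
- Progression in target lesions needs at least a 20% rise from the smallest sum, and at least 5 mm in absolute terms (11.2.3).
- Without diameters neither can be computed, and stable disease, which is defined by exclusion of both, cannot be assigned.
- Two routes remain: a lesion measurable by calipers or chest x-ray, or progression called on a new lesion. Hence the wording that such a patient *generally* has no valid measurement.

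**3. Size**

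- Section 13.0 plans 20 evaluable patients and applies the MRI evaluability rule to the secondary objectives as well, so the denominator for 2.2.4 is at most 20.
- It will probably be smaller: Section 4.1.2 admits non-measurable disease, and footnote e covers only patients with systemic disease.
- One patient lost is 1/20 = 5% at the largest possible denominator, and more at any smaller one.
- The protocol gives no basis for the number of patients who would have PET without a qualifying CT.

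**4. Tumour marker**

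- No marker appears in the laboratory lists of Sections 10.1 and 10.1.1 or in the calendar. Scheduled data therefore cannot show whether a marker was raised at the start or later became normal.
- Effect in measurable disease: the response table under Section 11.1.4 (printed in the CNS part) scores target CR with non-target Non-CR/Non-PD as PR. The patient stays a responder and only the CR/PR split moves.
- Effect in non-target-only disease: Section 11.2.1 puts these patients in a separate evaluability category, outside objective response.

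**5. Scan timing**

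Section 11.2 says "subjects should be re-evaluated every 4 cycles of treatment"; footnote e says every 12 weeks. With 21-day cycles, 4 × 21 = 84 days, and 84/7 = 12 weeks. The nominal intervals are identical.

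If a Day 8 dose is given on Day 15, Section 7.2 says to "initiate the next cycle no sooner than 2 weeks later". Day 15 + 14 = Day 29, which makes a 28-day cycle. For k such cycles, the days to the end of cycle 4 are (4 − k) × 21 + k × 28:

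- k = 0: 84 days
- k = 1: 63 + 28 = 91 days, inside the ±7-day window of Section 10.1.1
- k = 2: 42 + 56 = 98 days, 14 days after day 84 and so 7 days beyond the window

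**The case against.** The strongest reply is that the protocol already contains the safeguard. Section 11.1.3 sets the diagnostic-CT condition and the same-method rule, and the calendar lists contrast CT first. A site that reads the whole protocol would not rely on PET alone for RECIST. The objective is secondary and descriptive, with no hypothesis or decision rule attached. This limits the importance of the point. It does not remove the inconsistency, because the three schedule entries omit the condition and Section 11.1.4 names a narrower modality than they do.

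Three stronger readings are tempting, and the documents do not support them.

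- **Systemic response cannot be scored for patients followed by the calendar.** This is too broad. Contrast CT, or PET-CT with a documented diagnostic CT, also complies with the calendar and supports PR, SD and PD.
- **The two scan intervals conflict, by up to 4 weeks.** The 4-week figure needs four delayed cycles (4 × 28 = 112 days, or 16 weeks). The dose-reduction table in Section 7.2 steps down after each Day 8 delay and ends in discontinuation. A patient starting at 1.4 mg/m² reaches discontinuation at the third delay, so about two lengthened cycles (98 days) is the most this route gives. What remains is that the plan does not say which clock governs after delays. Section 7.2 states no maximum for a Day 1 delay, so a hold of more than a week there could also separate the two clocks.
- **A stated share of the sample will be lost.** Nothing in the documents indicates how many patients would have PET alone.

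**Conclusion.** The point holds for PET. Three schedule entries accept FDG PET unconditionally, while the measurement sections either omit it or admit PET-CT only with a documented diagnostic-quality contrast CT. A patient who complies with the calendar can therefore be unscorable for objective 2.2.4.

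The size is at least 5% of the systemic response denominator per affected patient, and the number affected is unknown. This assumes that the PET performed has no qualifying CT component and that no lesion is measurable by another listed method. CNS PFS by MRI, the primary endpoint, is not touched.

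The missing tumour marker is a minor gap that mainly affects the split between CR and PR. A reader might infer that it decides who counts as a responder. The separate evaluability category in Section 11.2.1 and the PR rule in the response table do not support that for the objective response rate. Scan timing is not a conflict and needs at most one clarifying line.

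**What to change.** 1. In Sections 10.1, 10.1.1 (Cycles 4+) and 10.2, including footnote e, replace the imaging item with: contrast-enhanced CT of chest, abdomen and pelvis, or PET-CT whose CT component the site has documented as diagnostic quality with IV contrast (see 11.1.3); same modality at baseline and follow-up.
2. Align the sentence on systemic imaging in Section 11.1.4 with that wording.
3. In Section 11.2.3, either remove the tumour marker condition from the non-target categories or add the marker to the screening and follow-up schedule. Either closes the gap.
4. Optionally, state in Section 11.2 that systemic scans follow the 12-week calendar clock, with the existing ±7-day window, when cycles are delayed.

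Items 1, 2 and 4 are wording changes. Their cost is that a few patients would have the contrast CT already listed instead of PET alone. Under item 3, removing the condition changes the CR definition, while scheduling a marker adds a laboratory test.
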